## **Study Protocol**

Therapy will be administered to participants through a mobile application which all participants in the experimental group will use at home for two weeks. Before starting the use, pre-tests are conducted to determine the baseline scores of language function and communication using the Barcelona test and the Communicative Activity Log. In the introductory session, after the tests, the application is installed on the participant's own phone and the participant is given instructions and trained in how to use the application, before starting their individual use of it at home. The therapist will prescribe use of the application 2 times per day for 20 minutes. Support is made available during the two weeks, if the participant is having issues with the use of the application. Furthermore, all patients are informed that they are allowed to receive help from family members or others in using the application at home.

The participant is instructed to use the application two times every day for about twenty minutes, but although this was the recommended use, the participant is free to use the application when and for as long as they want. While using the app, the participant will, through the app, be informed when they have been practicing for twenty minutes, in order to limit their use to shorter but more frequent sessions. The practice consists of several different tasks that are connected to different contexts from everyday life. The tasks consist of matching visual objects, sounds, and short videos, as well as some written input of words. The tasks also ask participants to record their voice saying the name of the object and to listen to and evaluate their recording.

After two weeks, the participants will return and be given post-tests on the same measures as before the start of the treatment, i.e., clinical scales for assessing language function and communication. Additionally, they will complete two usability questionnaires (the System Usability Scale and the mHealth App Usability Questionnaire), and a few questions regarding risk assessment.

The control group will also receive the pre-tests on the first day and post-tests 14 days later. They will not receive any treatment in that period, and they are not instructed to do or not to do anything in particular while at home. This means that the control group participants will proceed with their daily life as normally. The usability questionnaires will only be administered to the experimental group, not to the control group.

## **Plan for Statistical Analysis**

The analysis of the Barcelona test and the Communicative Activity Log (CAL) will consist primarily of within-group analyses with the Wilcoxon rank sum test, because of the low number of subjects. Additionally, linear mixed effects models will be used for the between-group analyses, with the Barcelona Test and the CAL score for each domain (patient, family, and therapist), respectively, as the dependent variable. The main independent variable will be the pre-/post-test (time) through binary coding, as well as the control versus the experimental group, including the interaction between the time variable and the group. The participant ID will be included as random intercept in the model, to account for differences between participants. The validity of the regression analysis will be evaluated by testing the residuals of the model for normality using the Shapiro-Wilk test for normality. Given the low number of subjects, the descriptive statistics will be reported with medians and quartiles, as with non-parametric tests.

A descriptive analysis will be made of the SUS and MAUQ usability questionnaires to determine the potential of a mobile application by drawing general conclusions from the use of this specific application. These will be analysed with computation of overall scores and examination of scores of different qualities of the application and use.

Further analysis will consist of descriptive statistics of the use of the application, e.g., amount of use, reaction times, and recording length, for participants in the experimental groups. The variables will be checked for normality with the Shapiro-Wilk test and depending on the results either means and standard deviation or medians and quartiles will be reported. The use measures will be analysed with t-tests or Wilcoxon rank sum tests to evaluate whether they changed over time with the use of the application.

An additional analysis will be made of the score differences for the Barcelona test of the experimental group, where the amount of use will be included in a linear regression model. With the difference in test score as the dependent variable, the independent variables included will be the total amount of use of the application. This analysis will evaluate whether the amount of use influenced the outcome of the treatment.

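### The leading analysis is pre/post change within each group; the comparison with the untreated control group comes second, so change shared by both groups can be read as an app effect.

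*Combined protocol and SAP*

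**What the plan says.** In the first paragraph of the Plan for Statistical Analysis, the work on the Barcelona test and the CAL "will consist primarily of within-group analyses with the Wilcoxon rank sum test, because of the low number of subjects". The next sentence brings in the control group: "Additionally, linear mixed effects models will be used for the between-group analyses". That model has a random intercept per participant, a binary term for time and a term for group, "including the interaction between the time variable and the group".

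The Study Protocol describes a concurrent control. "The control group will also receive the pre-tests on the first day and post-tests 14 days later", and of the same participants it says "They will not receive any treatment in that period". The app group is likewise to "be given post-tests on the same measures as before the start of the treatment". Both groups therefore take the same tests twice, two weeks apart.

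The plan does not say which result decides whether the app worked, or that the time-by-group interaction is the estimate of the app effect. It states no alpha and no success rule.

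**The concern.** The change from pre-test to post-test in the app group is the sum of two things: whatever the app did, and whatever would have happened anyway. The second part includes practice on tests taken two weeks before, and possibly spontaneous recovery or regression to the mean. A within-group test cannot split that sum at any sample size. The control group is there to measure the second part, yet the leading analysis leaves it aside.

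Running the within-group test in both groups and noting that one is significant and the other is not does not help. A difference between two p-values is not a test of the difference between two changes.

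The reason given is the low number of subjects. Small numbers can justify a rank-based method. They do not justify putting the control comparison second, because a rank test can compare change scores between groups just as well.

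At stake is whether the leading result bears on the app at all. If both groups improve on retest, a significant change in the app group could head the report while an unremarkable interaction sits below it.

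**Working it through.** **No figure to reproduce.** The documents give no sample size, alpha, effect size, SD or pre/post correlation. Everything below is an illustration under stated assumptions.

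**Assumptions.** No true app effect; 10, 15 or 20 per group; two-sided 0.05; change scores Normal(d, 1) in both groups, so the shared gain d is in SDs of change.

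**Step 1: what each analysis estimates.** Let S be the shared change and A the app effect.

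- Within the app group: mean change = S + A.
- Within the control group: mean change = S.
- Between groups: (S + A) − S = A.

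Only the third isolates A.

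**Step 2: false signals when A = 0.** Simulation, 20,000 runs per cell. The first two rate columns use the paired signed-rank test within groups. The last is the exact rank sum test on post-minus-pre change between groups. Entries are for n = 10 / 15 / 20 per group.

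| Shared gain d | App group significant | App significant, control not | Between-group test |
|---|---|---|---|
| 0 | 5% / 5% / 5% | about 5% | 4% to 5% |
| 0.3 | 13% / 18% / 24% | about 12% / 15% / 18% | 4% to 5% |
| 0.5 | 29% / 42% / 55% | 20% / 24% / 25% | 4% to 5% |
| 0.8 | 60% / 80% / 91% | 24% / 17% / 8% | 4% to 5% |

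The third column follows from the second. The groups are independent, so its rate is p(1 − p), where p is the within-group rejection rate. At d = 0.5 and n = 20 this is 0.55 × 0.45 = 0.25, which is also its maximum. At d = 0.8 it falls (0.91 × 0.09 = 0.08) because both groups become significant.

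A two-sample t-test on change, equivalent to the planned interaction with two time points and complete, balanced data, stayed at 4.5% to 5.3% for 10 to 30 per group and d from 0 to 1.0.

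**Step 3: the test as literally named.** The rank sum test is for independent samples. Applied to pre versus post scores, it ignores the pairing and usually rejects less often. At d = 0.5, with no app effect:

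| Pre/post correlation | n = 10 | n = 15 | n = 20 |
|---|---|---|---|
| 0.9 | below 0.5% | below 0.5% | below 0.5% |
| 0.7 | 3% | 6% | 10% |
| 0.5 | 10% | 18% | 27% |

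It still responds to S and still does not compare the groups.

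**Step 4: which mixed-model term is the app effect.** In one simulated data set with 15 per group, mean change was 0.33 in controls and 0.60 in the app group. The time coefficient was 0.33 with control as reference, 0.60 with app as reference, and 0.47 with group coded −0.5/+0.5. The interaction was 0.60 − 0.33 = 0.27 in size each time. Coding both factors −1/+1 only rescales the interaction, to a quarter of that difference. The time term, by contrast, changes meaning with the coding, so the plan has to name the interaction.

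**Step 5: cost of the between-group contrast.** With equal SDs of change, the ratio of 95% interval widths is

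[t(2n−2) × √(2/n)] ÷ [t(n−1) × √(1/n)] = √2 × t(2n−2) / t(n−1).

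- n = 10: 1.414 × 2.101 / 2.262 = 1.31
- n = 15: 1.414 × 2.048 / 2.145 = 1.35
- n = 20: 1.414 × 2.024 / 2.093 = 1.37

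Power of the rank sum test on change at n = 10 / 15 / 20 is about 36% / 53% / 67% for an app effect of 0.8 SD of change, and 51% / 72% / 85% for 1.0 SD.

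**The case against.** The strongest reply is that the right contrast is already planned. The mixed model contains the interaction, is labelled as the between-group analysis, and covers the Barcelona test and each CAL domain. The proper estimate will be produced whatever it is called. The plan also sets no success rule and never says that a within-group result will count as proof of the app; its word for the ranking may mean only that most of the analyses are of this kind. Comparing significance between groups is not a stated rule either.

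All of this is true, and it limits the point to ranking and labelling. It does not remove it. On either reading the control comparison stands second, and nothing ties a conclusion about the app to the interaction.

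A second reply is that the larger percentages come from the signed-rank test, which the plan does not name. That is fair. On the literal reading the rates are lower, and below 5% when pre and post scores are highly correlated and the gain is moderate. That changes the size of the false signal, not the fact that the test leaves out the control group.

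Third, the shared gain is assumed. With none, the within-group test holds its 5%. Spontaneous recovery and regression to the mean are possibilities here, not facts shown by the documents. Repeat testing on the same measures is a fact.

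**Conclusion.** The concern holds. As written, the leading analysis cannot separate an app effect from change common to both groups, although the trial collects the data to do so, and small numbers do not justify that order. The logical point needs no assumption. The size does: at a shared gain of 0.3 to 0.8 SD of change and 10 to 20 per group, a paired within-group test would be significant in 13% to 91% of trials of an app with no effect, against 4% to 5% for a between-group test of change. This should be corrected before analysis, because it decides whether the headline result is evidence about the app.

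**What to change.** Make the between-group comparison of change primary and choose its form in advance. Either the planned time-by-group interaction or an exact Wilcoxon rank sum test of post-minus-pre change between groups will serve; the second keeps the rank-based approach that the small numbers call for. State that this contrast, with its 95% interval, is the estimate of the app effect. Report within-group results as descriptive, without a conclusion about the app.

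Add the limits of the contrast. It removes shared change only. It does not remove expectation effects, since the control group is untreated, or differences between the groups that arise from how they were allocated.

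The cost is a change of SAP wording; both groups' pre and post scores are already to be collected. The real downside is the wider interval and modest power shown above, so the headline may be less favourable. An imprecise estimate of the app effect is still more useful than a tighter estimate of a mixture.

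### The primary within-group pre/post analysis names the Wilcoxon rank sum test, an independent-samples test, for paired data

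*Combined protocol and SAP*

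**What the plan says.** The first paragraph of the Plan for Statistical Analysis gives the leading role for both outcome measures to "within-group analyses with the Wilcoxon rank sum test, because of the low number of subjects". Mixed models for the between-group comparison come in addition.

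The Study Protocol describes the measurements. In the experimental group, after two weeks, "the participants will return and be given post-tests on the same measures as before the start of the treatment". For the other arm, "The control group will also receive the pre-tests on the first day and post-tests 14 days later".

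Elsewhere the plan treats the scores as repeated measurements. For the mixed model, "The participant ID will be included as random intercept in the model, to account for differences between participants". The regression on amount of use is set up "With the difference in test score as the dependent variable". The rank sum test is named once more, in the third paragraph, for app-use measures: "t-tests or Wilcoxon rank sum tests to evaluate whether they changed over time". The words paired and signed-rank do not appear anywhere.

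**The concern.** Within one group the only contrast available is pre against post, and both scores come from the same people. The rank sum (Mann-Whitney) test pools the two sets of scores and ranks them as if they came from different people. A participant who is mildly impaired at both visits and one who is severely impaired at both visits then add spread that hides the change, although that spread has nothing to do with change. The signed-rank test works on each person's difference and removes it.

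What is at stake is the analysis on which the plan chiefly relies, in a study that describes its own numbers as low. A real change could be missed. The rank test and the mixed model could also disagree on the same data only because one ignores the pairing. If the test were changed after the data had been seen, it would look like a post hoc choice.

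**Working it through.** **Inputs from the documents.** The named test and its primary role come from the Plan for Statistical Analysis, first paragraph. The paired design of both arms comes from the Study Protocol. The documents give no sample size, alpha, effect size, SD or pre/post correlation, so there is no figure of the plan's own to reproduce.

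**Assumed inputs.** Bivariate normal scores with SD 1 at each visit, two-sided 5% level, exact null distributions for both tests, n = 10, 15 or 20 per group, and a range of correlations ρ.

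**Why the correlation decides the matter.** With score variance σ², the mean change has variance 2σ²(1 − ρ)/n. An independent-samples test works as if it were 2σ²/n. The ratio of true to presumed variance is 1 − ρ: 1 at ρ = 0, 0.5 at ρ = 0.5 and 0.3 at ρ = 0.7. The test therefore uses too wide a yardstick whenever ρ > 0.

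**Power, raw change fixed at 0.5 SD (simulation; rank sum vs signed-rank).**

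| ρ | n = 10 | n = 15 | n = 20 |
|---|---|---|---|
| 0 | 16% vs 17% | 24% vs 24% | 32% vs 31% |
| 0.5 | 10% vs 29% | 18% vs 42% | 27% vs 55% |
| 0.7 | 8% vs 43% | 14% vs 62% | 24% vs 76% |
| 0.9 | 5% vs 86% | 10% vs 97% | 19% vs 99.6% |

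At ρ = 0.3 and n = 15 the figures are about 20% vs 31–32%. All cells carry Monte Carlo error of up to about one percentage point.

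**Power, change fixed at 0.8 SD of the change score.** The raw change is 0.8 × √(2(1 − ρ)): 1.13 SD at ρ = 0, 0.80 at 0.5, 0.62 at 0.7 and 0.36 at 0.9. At n = 15, signed-rank power stays at 80% by construction. Rank sum power is 82% at ρ = 0, 70% at 0.3, 54% at 0.5, 28% at 0.7 and 2% at 0.9. The loss thus appears under either scaling of the effect.

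**Type I error of the rank sum test at nominal 5%.** It is 4.4% to 4.9% at ρ = 0, about 2% at 0.3, about 1% at 0.5, and 0.2% or lower from 0.7. The signed-rank test stays close to 5% throughout. Only under negative correlation does the rank sum test exceed its level (6.9% to 7.6% at ρ = −0.3).

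**Worked example (hypothetical data).** Ten participants have pre-scores 10, 20, ..., 100 and improve by 3, 4, 5, 6, 7, 8, 2, 9, 1 and 4.5 points.
- Rank sum: every change is below 10, so each post-score lies above the person's own pre-score and below the next person's. The number of post/pre pairs with post higher is 10 + 9 + ... + 1 = 55 of 100, against 50 expected under no change. Hence U = 45 (the smaller of 45 and 55), exact p = 0.74.
- Signed-rank: all ten differences are positive, so exact p = 2/2¹⁰ = 0.002.

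Everyone improves, and the test as named sees almost nothing.

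**The case against.** The strongest reply is that this is a naming slip. Authors who fit a participant random intercept and regress individual score differences probably meant the paired rank test. That is plausible. But the same name recurs in the third paragraph for change over time, and no wording points to a paired test. The documents leave it open, and a programmer who followed the text would run the wrong procedure.

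It is also fair to say that every power figure rests on assumed inputs. Only the direction is established, and only for positive correlation. The worked example is close to an extreme case. In the scenario scaled to the change score, the raw shift shrinks as correlation rises, so its most dramatic figures should not be read alone.

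Third, the error does not touch the estimate of the treatment effect, which is the time-by-group interaction in the mixed model. Under positive correlation it does not inflate false positives either. Both points stand, and they limit the harm to missed change within an arm. The mixed model does not fully substitute for the primary test, however. At n = 15 per group and a change of 0.8 SD of the change score, its time contrast in the experimental group has about 85% power, but the interaction, which is what the plan assigns to it, has about 56%.

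**Conclusion.** The concern holds. As written, the plan applies an independent-samples test to paired data in the analysis it calls primary, and this is inconsistent with how it handles the same scores elsewhere. That conclusion needs no assumption beyond the text.

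The size of the consequence depends on the pre/post correlation. There is no loss at 0 and a modest one at 0.3. At n = 15 and a 0.5 SD change, power falls by 24 points at 0.5 (42% − 18%) and by 48 points at 0.7 (62% − 14%). Positive correlation is the natural expectation for the same people on the same scales two weeks apart, and a participant random intercept presumes it. The error leads to missed change and not to spurious change. It should be corrected before any data are analysed, because it concerns the primary test and costs almost nothing to put right.

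**What to change.** In the first paragraph of the Plan for Statistical Analysis, replace the rank sum test with the Wilcoxon signed-rank test on each participant's pre/post difference, for the Barcelona test and for each CAL domain. The plan lists the domains only for the mixed models, so the rank analysis should name them too. Leave the between-group comparison to the planned mixed model.

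Two secondary details are worth adding at the same time:
- state that p-values are exact or by permutation, and how ties and zero differences are handled;
- for the app-use measures in the third paragraph, state the unit of analysis and the time contrast. If one early and one late value per participant are compared, name a paired t-test or the signed-rank test.

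The main correction takes one or two sentences and no extra data. If the signed-rank test was always intended, only its name changes.

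### The CAL ratings are tested on the same footing as the Barcelona test, so expectation in an unmasked comparison with no treatment can appear as benefit both within and between groups

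*Combined protocol and SAP*

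**What the plan says.** The first paragraph of the Plan for Statistical Analysis treats the Barcelona test and the CAL together. Their analysis "will consist primarily of within-group analyses with the Wilcoxon rank sum test, because of the low number of subjects". Mixed models are then added for the between-group comparison, "with the Barcelona Test and the CAL score for each domain (patient, family, and therapist), respectively, as the dependent variable", with time and group as predictors, "including the interaction between the time variable and the group", and a random intercept per participant. No outcome is named as primary, and nothing says how a CAL difference without a Barcelona difference would be read.

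The Study Protocol describes what each group experiences. In the experimental group "the application is installed on the participant's own phone and the participant is given instructions and trained in how to use the application". On prescription: "The therapist will prescribe use of the application 2 times per day for 20 minutes". On help at home: "all patients are informed that they are allowed to receive help from family members or others in using the application at home". Of the controls it says: "They will not receive any treatment in that period, and they are not instructed to do or not to do anything in particular". No sham app or attention control is described. The documents do not mention masking of the CAL raters or of whoever gives the Barcelona test.

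**The concern.** The CAL domains are labelled patient, family and therapist. On the natural reading, these are the people who give the ratings. An experimental patient knows that he or she used the app, and the family will usually know too. The protocol has a therapist prescribe it. In the control group the same kinds of rater will usually know that nothing was given. A rater who expects improvement may score the post-test higher although communication has not changed.

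Neither planned analysis protects against this. The within-group test has no comparator, so expectation counts as change, together with retest effects and natural change. The group-by-time term removes time effects common to both groups, but not a shift that differs between them. With no hierarchy in the plan, a significant CAL result could be reported as evidence of efficacy alongside, or in place of, a result on a language test.

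**Working it through.** **Inputs from the documents.** There are four scores (Barcelona and three CAL domains), two time points, two groups, a random intercept per participant, a group-by-time interaction, and primary within-group tests. The documents give no sample size, significance level, SD or effect size, so there is no planned figure to reproduce.

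**Where the shift goes.** Let δ be the true treatment effect, τ the change over two weeks common to both groups (retest, natural change), and b_E and b_C the expectation shifts in the rated change of the experimental and control groups.

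- Within the experimental group, expected change = δ + τ + b_E.
- With two time points and complete data, the interaction equals the difference in mean change: (δ + τ + b_E) − (τ + b_C) = δ + (b_E − b_C).

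The equality was checked on one simulated data set with 15 per group: the mixed model gave 0.733 (SE 0.218) and the difference in mean change 0.733 (SE 0.218). The interaction removes τ but keeps b_E − b_C in full. The within-group test keeps τ as well as b_E. No term in the model separates δ from the shift.

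**Illustration of size.** Assumptions, none taken from the documents: δ = 0, τ = 0, b_C = 0, b_E = b = 0.3 or 0.5 SD of the change score, equal groups of n = 10, 15 or 20, and a two-sided 5% test, so 2.5% in the direction of benefit.

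- Between groups: t on 2n − 2 df with noncentrality b√(n/2). Example, n = 10, b = 0.3: 0.3 × √5 = 0.671, critical value 2.101 on 18 df, upper-tail probability 0.093.
- Within the experimental group: one-sample t on n − 1 df with noncentrality b√n, standing in for the planned Wilcoxon test. Example, n = 10, b = 0.3: 0.3 × √10 = 0.949, critical value 2.262 on 9 df, upper-tail probability 0.134.

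| n per group | Between, 0.3 SD | Between, 0.5 SD | Within, 0.3 SD | Within, 0.5 SD |
|---|---|---|---|---|
| 10 | 0.093 | 0.184 | 0.134 | 0.293 |
| 15 | 0.122 | 0.262 | 0.190 | 0.438 |
| 20 | 0.150 | 0.338 | 0.246 | 0.564 |

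These are chances of a significant false benefit on one CAL domain. For the same shift the within-group test, which the plan puts first, is affected more than the interaction.

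**Three domains.** With a correlation of 0.5 between domains (also assumed), simulation with 20,000 runs per setting gives the chance of at least one significant false benefit between groups as 0.21, 0.26 and 0.31 for a 0.3 SD shift, and 0.37, 0.48 and 0.59 for 0.5 SD, at 10, 15 and 20 per group. With no shift it is about 0.06.

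**The case against.** The strongest reply is that much of this rests on what the documents leave unsaid, and several parts of that reply stand.

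- *Raters.* Nothing says outright who completes each CAL form, that the prescribing therapist is the rating therapist, or that any family rater helped; help is permitted, not assigned. Nor is it stated when the group becomes known, so a one-sided shift arising only at post-test is an assumption. If both groups' ratings shifted equally, the interaction would be unaffected. The point therefore rests on a natural reading of the labels and on the absence of any described masking.
- *Therapist domain.* A reader might infer that the therapist has no sight of the 14 days at home, so that this domain should leave the models. The documents do not support that. They do not describe what the therapist form asks, its recall period or its source of information.
- *Barcelona test.* A reader might infer that it is free of this bias. The documents do not say who gives it or whether that person knows the group. A performance test is usually less open to expectation than a rating, but that is a difference of degree.
- *Equal standing.* A reader might infer that the plan commits itself to reading a CAL difference as an app effect. It contains no such rule, and only the Barcelona score enters the amount-of-use regression. What stands is that the main analyses are identical and no ranking or caveat guides interpretation.
- *Size.* Both the shift and the group size are assumed. The figures show how error would grow, not that a bias of this size is likely.

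The reply does not remove the structural point: if rating expectation differs by group, neither planned CAL analysis can distinguish it from benefit.

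**Conclusion.** The concern holds in this form. The plan analyses the CAL domains and the Barcelona test identically and without hierarchy, in a comparison with an untreated group and with no masking described. Expectation can therefore appear as benefit in the within-group CAL tests and in the CAL group-by-time term. The actual bias cannot be estimated from the documents. Under the assumed shifts and group sizes, the false-benefit rate per domain is about 9% to 34% between groups and about 13% to 56% within group, the latter by t-test approximation to the Wilcoxon test, against 2.5%. The conclusion does not depend on those figures. It needs only that CAL raters generally know whether the app was used, which is likely but not stated. An open design may be unavoidable for an app of this kind, but how its rated outcomes will be interpreted can be fixed in advance. The change is worth making because it alters what the trial may conclude.

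**What to change.** In the first paragraph of the Plan for Statistical Analysis:

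1. State that the efficacy conclusion rests on the between-group (group-by-time) Barcelona result, and that this replaces the primarily within-group approach as the basis for that conclusion.
2. Keep all three CAL domains, including the therapist domain, in the analysis. Report both their within-group and their between-group results as open-label supportive outcomes that cannot on their own support a claim of benefit.
3. State that the Barcelona result carries the same caveat, in lesser degree, if its assessor knows the group.

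The cost is SAP wording only, with no extra participants, visits or staff. The downside is that a difference seen on the CAL alone could no longer be claimed as efficacy. The wording should be settled before results are seen, because a later decision to demote or keep a CAL finding would look selective.

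### Four outcomes are tested between and within groups with no primary outcome and no multiplicity adjustment, and the uncontrolled within-group tests are ranked ahead of the controlled comparison

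*Combined protocol and SAP*

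**What the plan says.** The Plan for Statistical Analysis describes two layers of efficacy analysis.

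- **First layer.** The analysis of the Barcelona test and the CAL "will consist primarily of within-group analyses with the Wilcoxon rank sum test, because of the low number of subjects".
- **Second layer.** The plan then adds a controlled comparison: "Additionally, linear mixed effects models will be used for the between-group analyses". One such model is fitted per outcome, which the plan expresses as "with the Barcelona Test and the CAL score for each domain (patient, family, and therapist), respectively, as the dependent variable". That is four models. Each contains time, group and their product, the plan's words being "including the interaction between the time variable and the group".

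The Study Protocol section gives the control group the same assessments: "The control group will also receive the pre-tests on the first day and post-tests 14 days later".

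Neither section names a primary outcome, a significance level, an adjustment for multiple tests, or a rule for reaching an overall conclusion from the results. The only ranking is by type of analysis: within-group first, between-group in addition. No outcome is placed above another in either layer. The use-response regression takes the Barcelona score change as its only outcome, but the plan does not call that outcome primary.

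**The concern.** There are two linked problems.

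1. **Multiplicity.** With four outcomes and two types of analysis, a reader of the results cannot tell which test was meant to answer the efficacy question. The probability that something reaches significance by chance exceeds the nominal level of any one test. Three of the four outcomes are CAL domain scores from different sources, and nothing in the plan says what follows if they disagree.

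2. **Ranking.** The analyses placed first make no use of the control group as a comparator. Both groups repeat the same tests after two weeks, so change within the experimental group mixes any effect of the app with retest gain and other change over that period. The time-by-group interaction separates these, and the plan makes it additional.

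What is at stake is whether the efficacy conclusion rests on one controlled, pre-declared test or on a selection from several, some of them uncontrolled.

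**Working it through.** **No stated figure to reproduce.** The documents give no sample size (only that the number of subjects is low), significance level, power or error rate.

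**Inputs from the documents**
- Between-group tests: 4 (Barcelona; CAL patient, family and therapist), one interaction each.
- Within-group tests: the sentence names the Barcelona test and the CAL without restating the domain split, so 2 to 4 per group. Testing in both groups is implied by the plural and by the control group's repeat assessments, but is not written.
- Total: 4 + 2 = 6 at the fewest, 4 + 4 + 4 = 12 at the most. The models' time and group main effects, the tests on use measures and the use-response regression are not counted.

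**Assumptions**
- Two-sided 5% per test.
- 10, 15 or 20 participants per group.
- Correlation among the four outcomes from 0 to 0.9.
- Pre/post correlation 0.8, with one check at 0.5.
- No true change in either group.

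**Closed form for k independent tests:** 1 − 0.95^k.
- k = 4: 1 − 0.95^4 = 0.185.
- k = 12: 1 − 0.95^12 = 0.460. This is only a ceiling, because the between-group statistics are built from the same change scores as the within-group ones.
- Favouring the app only, k = 4: 1 − 0.975^4 = 0.096.

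**Simulation** (4,000 trials per setting). The interaction is tested as a t-test on change scores, which is equivalent with complete data at two time points. Within-group tests are run as the paired signed-rank test, then as the unpaired rank sum test that the plan names. Entries are the percentage of trials with at least one p < 0.05, as a range over the three group sizes. The 8 tests are the experimental within-group tests (paired) plus the interactions.

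| Outcome correlation | 4 interactions | 12 tests, paired | 12 tests, unpaired as worded | Favouring app, 4 interactions | Favouring app, 8 tests |
|---|---|---|---|---|---|
| 0 | 18.1–19.6 | 38.0–38.9 | 18.2–19.7 | 9.5–10.0 | 15.2–16.0 |
| 0.3 | 16.6–17.7 | 35.3–36.6 | 16.8–17.8 | 8.2–9.2 | 13.4–14.2 |
| 0.5 | 15.1–16.4 | 32.5–33.8 | 15.1–16.5 | 7.1–8.5 | 11.4–13.0 |
| 0.7 | 13.1–13.9 | 28.2–29.5 | 13.2–13.9 | 6.5–6.7 | 9.9–11.1 |
| 0.9 | 9.4–10.2 | 20.6–22.9 | 9.5–10.3 | 4.8–5.4 | 7.4–8.4 |

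A separate simulation of 400,000 draws of correlated normal statistics gives 17.4%, 15.5% and 13.0% for the four interactions, and 36.3%, 32.8% and 27.7% for 12 paired tests, at correlations 0.3, 0.5 and 0.7.

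**Why the unpaired column is lower.** Applied to two measurements on the same people, the rank sum test ignores their positive correlation. Each such test rejected at most about 0.1% of the time at pre/post correlation 0.8, and 0.9% at 0.5. The within-group tests then add almost nothing to the error rate. For the same reason they would also have little power.

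**Comparator for the favourable direction.** One two-sided 5% test spends 2.5% there. Four interactions give 4.8/2.5 = 1.9 to 10.0/2.5 = 4 times that. Eight tests give 7.4/2.5 = 3.0 to 16.0/2.5 = 6.4 times.

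**The case against.** Several points on the other side are sound.

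- **A reader might infer that a false claim of benefit is several times more likely than 5%.** The figures do not support that. The larger percentages count significance in either direction and include control-group tests, which cannot show that the app works. Restricted to results favouring the app, the chance is about 5 to 16%, or roughly 1 to 3 times 5%. The multiple is larger only against the 2.5% that a single two-sided test spends in that direction.
- **A reader might take 12 as the number of tests.** The documents fix only four. The CAL split is written for the mixed models alone, and testing within the control group is implied.
- **A reader might infer that any one significant result, or the most favourable CAL domain, may be reported as an effect of the app.** The plan contains no such rule. It has no success rule at all, and that is the gap.
- **Taken literally, the within-group tests barely inflate the error rate**, because the named test is unpaired. This stands, but it follows from a test that does not suit paired data.
- **The trial is small, and formal error control may seem out of place.** The documents do not label it exploratory, and they plan formal between-group models and an analysis of whether use affected the treatment outcome. Small numbers favour concentrating inference on one contrast, which keeps its full 5% and needs no additional participants.

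None of this supplies a primary outcome, or a reason to rank uncontrolled comparisons ahead of controlled ones.

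**Conclusion.** The point holds in a limited form. The count of four unadjusted between-group tests is explicit and depends on no inference. At an assumed two-sided 5% level, their chance of at least one false-positive significant result is 18.5% if independent, and about 9 to 17% at outcome correlations of 0.9 to 0.3. So even highly correlated outcomes give about twice the nominal rate.

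Extending to as many as 12 tests gives about 21 to 39% if the within-group tests are paired and about 10 to 20% as worded. Those ranges rest on a partly inferred count and on assumed group sizes and correlations.

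All these figures, including those for results favouring the app, assume no change in either group. Retest gains would raise the within-group part, but the documents give no size for them, so that is not quantified.

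The ranking problem does not depend on the simulation. As written, the main analysis cannot separate the app's effect from change that would have occurred without it.

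**What to change.** Add to the Plan for Statistical Analysis, before any data are seen:

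1. **One primary test.** The efficacy conclusion rests on the time-by-group interaction for one named outcome at two-sided 5%. The Barcelona test is a natural candidate, since it is already the sole outcome of the use-response regression, but the choice is the sponsor's. If it is chosen, define which Barcelona score is used, because the documents do not say.
2. **Remaining between-group tests.** Treat the other three outcomes as secondary with Holm adjustment, or label them exploratory. If Holm is used, state whether these tests are made only when the primary test succeeds. Without that condition the primary and secondary families each carry 5%, and together up to 5% + 5% = 10%.
3. **Within-group change.** Report it descriptively for both groups, without efficacy claims.

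The cost is a few sentences, since the model is already planned. There are two downsides. A secondary outcome needs a smaller p-value, 0.05/3 = 0.0167 at the first Holm step. The interaction is also less precise than a within-group change: with equal group sizes and variances its standard error is √2 ≈ 1.41 times as large. That is the price of a controlled comparison.
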